1. SPECIFIC AIMS

Continued tobacco use among cancer survivors (hereafter called survivors) is a cause of second primary cancers and high mortality.^{1,2} Despite greater acute health risks from resuming smoking for individuals with cancer, smoking prevalence among survivors is higher than, or comparable to, those without a cancer history.³ Importantly, regardless of the high quit rate at cancer diagnosis,⁴ more than half of survivors who attempt to quit resume smoking within a few months.⁵ Notably, existing smoking cessation trials for survivors have not demonstrated consistent results.⁶ Such results might be due to a lack of understanding in the dynamic relation between cancer-specific (e.g., fatigue, pain, fear of cancer recurrence) and general smoking processes (e.g., negative affect) contributing to smoking relapse in real-time.⁴ Given the prominent role of distress as a predictor of smoking relapse^{7,8} and chronic distress among survivors,⁹ it may be more challenging to reduce the effect of distress on smoking in this population vs the general population. Importantly, the synergistic effect of cancer-specific and general smoking vulnerabilities are linked to a higher likelihood of relapse.^{5,10-12} Given the projected 31.4% increase in the number of survivors by 2030,⁹ there is an urgent need to develop targeted, accessible, and scalable smoking cessation interventions for survivors to improve quality of life and decrease mortality.

Mindfulness-based interventions (MBIs) have great potential to enhance tobacco abstinence. MBIs have demonstrated efficacy among general smokers for craving and relapse.¹³ The primary mechanism of MBIs is the weakening of the association of distress and smoking through enhanced self-regulatory processes.¹⁴ Although promising, there has been only 1 single-arm, feasibility study examining an MBI for smoking cessation among survivors, which consisted of 8 weekly 2-hour inperson group sessions.¹⁵ This time-intensive and in-person format of traditional MBIs has been identified as a barrier to access.^{15,16} It also fails to leverage treatment delivery in the real world where efforts to guit smoking take place. Using a mobile health (mHealth) approach may address both issues. However, little effort has been made to integrate the core therapeutic elements of MBIs with mHealth, which could constrain the processes of acceptance and awareness.¹⁷ Thus, an mHealth MBI for smoking cessation tailored for survivors, with an emphasis on the strategic delivery of practices and implementation of core therapeutic ingredients would enhance accessibility, target key mechanisms, lessen patient burden, and reduce cancer-specific cessation barriers for patients (e.g., shame, guilt). Further, including psychometrically sound measures to assess momentary changes of relapse vulnerabilities in real-time would aid in testing the efficacy of an mHealth MBI. The overall objective of this application is to develop a mindfulness-based ecological momentary intervention (mindEMI) for smoking cessation for survivors.

Aim 1. To develop a mindfulness-based EMI (mindEMI) targeting cancer-specific smoking vulnerabilities through an iterative multi-step process. Three phases are planned: (1) In-depth qualitative interviews with 15 survivors on their perception of existing mHealth MBI approaches and feedback on the utility and acceptability of key MBI practices (e.g., breathing meditation, brief mindfulness strategies); (2) Create an initial draft of the intervention

Aim 2. To pilot test the mindEMI among cancer survivors. We will obtain feedback from another 10 survivors who will pilot the prototype of mindEMI that will deliver the MBI in real-time at both random moments and when high levels of smoking vulnerability are self-reported via EMA. The primary outcomes will be participants' open-ended feedback along with perceived utility and likability of the mindEMI and retention through the end of treatment.

This novel cessation intervention and demonstration of key feasibility and acceptability benchmarks, combined with the focused training plan, will lead to a future R01 trial of mindEMI for smoking cessation tailored for survivors. Ultimately, the intervention will dismantle cancer-specific and general risk factors of smoking relapse, with high accessibility, scalability, and the ability to intervene in real-time, thus increasing effect.

2. BACKGROUND AND SIGNIFICANCE

2.1. Cancer and Smoking

Continued smoking after a diagnosis of cancer is linked to an increased risk of lowered effectiveness of cancer treatment, cancer-related mortality, developing a secondary primary cancer, worse guality of life,^{18,19} and increased cancer treatment costs (\$3.4 billion/year).²⁰ Despite greater acute health risks of resuming smoking, higher smoking prevalence is observed among cancer survivors ("survivors") than those without a cancer history.^{3,21} Among those who make a quit attempt after cancer diagnosis (e.g., 31.4%),⁵ the relapse rate of over 50% is alarming.^{4,5} As such, promoting smoking cessation is recognized as an essential part of cancer care.^{22,23} However, the efficacy of smoking cessation interventions and strategies that are effective for general smokers has been minimal for survivors.^{6,24} This is likely due to a critical gap in the literature: Lack of understanding in real-time dynamic relations between cancer-specific (e.g., pain) and general smoking vulnerabilities (e.g., negative affect), which might synergistically increase the likelihood of smoking relapse.^{5,10-12} Given the impact of chronic distress in relapse,^{7,8} survivors may face a particular challenge with cessation. With the projected 31.4% increase in the number of survivors (i.e., 22.1 million) by 2030,9 there is an urgent need to develop targeted and scalable smoking cessation interventions for survivors with an emphasis on the interrelations between cancer-specific and general smoking vulnerabilities to improve mortality and quality of life.

2.2. Mindfulness and Smoking

[figure not shown]
Mindfulness-based interventions (MBIs) that cultivate awareness and acceptance of momentary experience^{25,26} are a promising approach to tobacco abstinence among survivors. From a theoretical perspective (e.g., Monitor and Acceptance Theory),²⁷⁻³⁰ MBIs are particularly efficacious for those in high stress situations, as MBIs can weaken the association between triggers (e.g., distress) and learned behaviors such as substance use, thereby reducing reactivity to triggers. This process occurs through purposefully paying attention, in a non-judgmental way, to the automatic cycle of triggers and present-moment experience. Among general smokers (i.e., non-cancer survivors), empirical evidence supports this theoretical framework by demonstrating a weakened association of craving and smoking³¹ through enhanced self-regulatory processes¹⁴ and decreased neural response to cigarettes³² and emotional cues,³³ leading to successful quitting.^{34,35} Notably, MBIs have demonstrated efficacy in enhancing smoking outcomes among general smokers for craving, relapse, ^{13,34-36} and abstinence.^{34,35,37,38} Nonetheless, MBIs for smoking cessation among survivors have been limited to 1 small-scale feasibility study conducted via in-person group treatment.¹⁵

There are at least 3 reasons why MBIs hold promise for survivors who continue to smoke. First, MBIs improve cancer-related psychological difficulties, implicating their potential in smoking cessation for survivors. Meta-analyses have shown that MBIs improve pain, fatigue, guality of life, fear of cancer recurrence, and sleep disturbance.³⁹⁻⁴¹ Further, in general population, mindfulness is positively associated with motivation to engage in behaviors because of genuine interest.⁴² Thus, MBIs may aid in managing cancer-related psychological difficulties that may interact with general smoking vulnerabilities, thereby facilitating guitting through enhanced motivation to sustain cessation efforts.³⁴ Second, MBIs may facilitate extinction of learned smoking behaviors (e.g., craving = grabbing a cigarette) by purposefully paying attention to the "autopilot" process of smoking (i.e., awareness), cultivating the ability to stay with craving and stress (i.e., acceptance), and enhancing self-regulatory processes, thereby attenuating the likelihood of smoking relapse.^{14,43} Survivors are more likely to face challenges in cessation because of the synergistic effects of cancer-specific and general smoking vulnerabilities, as indicated by a higher rate of continued smoking among those with a tobaccorelated cancer (vs other cancers)²¹ and higher smoking prevalence compared to those without a cancer history.^{21,44} Third, MBIs may alleviate cancer-specific cessation barriers such as guilt, shame^{4,5,10} among survivors. Contrary to other tobacco cessation approaches (e.g., cognitive

behavior therapy), MBIs put less emphasis on psychoeducation and skill-building and more on an individual's experiential learning. Although MBIs provide psychoeducational content, the focus is to cultivate resiliency to distress⁴⁵ through an inquiry-based learning process (i.e., explicit exploration of one's experience during mindfulness practices). Such process can aid in the reduction of guilt and shame by shifting in perspective (i.e., decentering) and taking a more objective perspective toward a given situation.⁴⁶

2.3. mHealth and Smoking

Smoking cessation interventions delivered via smartphone applications (apps) have flourished over the last 5 years⁴⁷⁻⁵³ and their feasibility and acceptability have been supported with high retention and abstinence rates among general smokers.^{48,50,52} A noted advantage of mHealth is the ability to deliver intervention content when it is most needed, such as the moment of vulnerability that precipitates lapse/relapse of smoking.⁵⁴ As revealed by ecological momentary assessment (EMA) studies among daily smokers, momentary risk factors of relapse include negative affect (NA),⁵⁵ urge,⁵⁵ positive affect (PA),⁵⁶ stress,⁵⁷ and the varying real-time dynamic relations of risk factors in the course of cessation efforts,⁵⁸ consistent with the Dynamic Model of Relapse in substance use.⁵⁹ Though data are limited, such momentary risk factors are highly likely to be amplified by cancerspecific smoking vulnerability (i.e., ecological momentary intervention [EMI]), the smoking abstinence would be facilitated. Figure 1 summarizes our conceptual framework that is informed by several theoretical models described above.^{27-29,59} Indeed, preliminary results from EMIs^{49,50} support this approach.

To date, there has been 1 full-scale randomized controlled trial (RCT) of an mHealth MBI for smoking cessation among general smokers,⁴⁷ in which a smartphone app provided 22 modules of an MBI in various forms (e.g., audio, video) for 22 consecutive days.⁶⁰ Notably, the association between

craving and smoking was significantly weakened in the MBI arm (vs inactive control) and cue reactivity decreased at the neuronal level, which was associated with reduced daily cigarette use.³² These promising results suggest that an MBI delivered via app is not only feasible but may also alter the strength of the association between craving and smoking at both behavioral and neuronal levels. However, biochemically verified abstinence at follow-up was not different between conditions, potentially because of a non-intended treatment component in the control condition (e.g., self-monitoring).⁴⁷ This app is currently being tested among young adult survivors,⁶¹ although it has not been tailored for survivors and does not incorporate EMI design or inquiry exercises,^{47,60} a key therapeutic component of MBIs that facilitates the learning process of acceptance and awareness.¹⁷ Given the more frequent mindfulness practice, the better cessation outcomes,³⁷ MBIs could be maximized by promoting the practice of mindfulness both briefly and regularly in the context of cessation in real-life, and when the vulnerable moment is captured by psychometrically sound items via EMA.

To the best of our knowledge, there are no mindfulness-based EMIs (mindEMIs) for smoking cessation specifically developed for survivors. Only 1 study has examined the feasibility of an MBI delivered in-person for smoking cessation among survivors.¹⁵ However, its time-intensiveness (weekly 2-hour in-person group sessions for 8 weeks) is not only a potential barrier to accessibility,^{15,16} but it also does not leverage treatment delivery in the real-world context where quitting takes place. Given the promising efficacy of MBIs using technology in improving quality of life in the general cancer population,³⁹ a mindEMI for smoking cessation tailored for survivors, with an

emphasis on both practice and inquiry-based learning processes, would not only enhance accessibility and target key smoking mechanisms, but also reduce patient burden.²²

2.4. Innovation

This study is highly innovative in several ways. First, this work will be among the first to integrate mHealth and MBIs for smoking cessation for survivors by retaining crucial theoretical and empirical components of MBIs (i.e., inquiry,¹⁷ acceptance and awareness,^{25,26} and formal meditation²⁶). In particular, this work will address a significant gap in the literature: (1) Developing MBIs targeting cancer-specific smoking vulnerabilities integrating extant theories^{27-29,59} and evidence from general smokers;⁵⁵⁻⁵⁸ and (2) leveraging unique windows of opportunity for intervention delivery (i.e., EMI)⁵⁴ in real time among survivors. Second, this work will be a novel mHealth MBI that integrates survivors' direct input in its development through gualitative interviews and an iterative process. Given the limited evidence on the efficacy of extant cessation strategies among survivors,⁶ the intervention design will be informed by survivors who will assess the utility of brief mindfulness strategies and formal mindfulness meditations. Thus, the proposed intervention is not only theoretically driven but also user-centered. Third, mindEMI would potentially maximize MBI efficacy for smoking cessation through the regular and momentary practice of mindfulness at key vulnerable moments in the realworld context, as evidenced by positive cessation outcomes through frequent mindfulness practice⁴⁷ and timely delivery of the intervention.^{49,50} Fourth, as compared to the intensiveness of traditional inperson MBIs, our proposed mHealth approach has high potential for scalability and costeffectiveness, thereby reducing cessation barriers for survivors.^{4,5,10} Fifth, EMA will be used to assess real-time data that capture both cancer-specific and general risk factors of smoking relapse to intervene, using psychometrically sound measures. To the best of our knowledge, EMA has not been widely used to examine smoking behaviors among survivors,⁶² although EMA has been used to assess other health behaviors, such as sleep among individuals with a cancer diagnosis.⁶³ Further, few EMA studies have tested the reliability of EMA scales used.^{55,64} Our study will provide a more accurate reflection of the dynamic relation between cancer-specific and general smoking vulnerabilities, informing future interventions for survivors.

3. PARTICIPANT SELECTION

3.1. Aim 1: Development

3.1.1. Participants

Interested participants will be screened over the phone and eligible participants will be scheduled for their interview. Inclusion criteria will include: (1) \geq 18 years old; (2) having smoked at least one cigarette (even one or two puffs) within the past 30 days; (3) having been diagnosed with cancer; (4) valid home address and functioning phone number; (5) being able to read, write, and speak English; and (6) having a smartphone. Smartphone ownership is not expected to be a barrier to recruitment given that 85% of Americans and 76% of low-income individuals own a smartphone.⁶⁵ Exclusion criteria will include (1) being enrolled in a smoking cessation program.

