3.1.2. Recruitment

Aim 1 will involve original data collection, conducted either in-person or remotely. Qualitative and quantitative data will be collected from cancer survivors to inform the development of mindEMI. Survivors who are current smokers will be recruited in 2 ways. First, using electronic medical records at Moffitt, a trigger that is configured in the electronic system will notify our study team weekly of patients who are classified as current smokers, and study staff will contact potential participants. This recruitment strategy has been successfully implemented by co-primary mentor, [name] research team^{66,67} (recruiting 4.6 cancer patients per month, who were interested in quitting but have

not completely quit, similar to the current proposal's sample characteristic).¹² She successfully recruited 7 and 12 cancer patients per month in her $R03^{12}$ and R01,⁶⁸ respectively and recruited one of the largest samples of this population in the literature to date (N = 412). Second, [name] team at the Cancer Survivorship Clinic at Moffitt will connect potentially eligible participants with the study team, and the study team will contact them.

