3.2. Aim 2: Usability Testing

3.2.1. Participants and Recruitment

Aim 2 will recruit 10 survivors, independent from Aim 1, to pilot the prototype mindEMI. Recommended sample size in usability studies is at least N=10 to capture 94.7% of potential usability problems, which guided the current sample size,⁶⁹ accounting for 30% drop out with a desired final sample size of 10 (will recruit N=13). Recruitment and eligibility will mimic Aim 1, with the addition of a few eligibility criteria. Additional inclusion criteria: (1) Willing to give quitting a try as part of the study; (2) Having a smartphone that allows installation of the app; and (3) Willingness to download and use the app daily. Additional exclusion criteria: (1) current use of smoking cessation medications (e.g., patch, gum, lozenge, nasal spray, inhaler, or any other nicotine replacement products or medications such as Chantix, Zyban, or Wellbutrin with the intent to quit smoking); (2) evidence of current psychosis; and (3) current/planning pregnancy or lactation. During the phone screen, we will ask participants to consult their physicians before nicotine patch use, if they endorse medical conditions (e.g., recent heart attack, heart disease, angina, high blood pressure not controlled by medications, stomach ulcer, diabetes type 1).⁷⁰

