mindEMI; QD+2W). During the week following the 3rd session (QD+3W), the end of treatment measures will be sent via REDCap and a brief phone interview will be conducted to collect feedback on mindEMI. Interviews will be audio-recorded and transcribed for content analysis. Smoking status will be measured using 7-day point prevalence of abstinence ([PPA]; no self-reported smoking in prior 7 days). The counseling sessions will be scheduled at/around the appointment that coincides with our timeline, remaining flexible if there may be medically related changes in schedules (e.g., unanticipated complications) or unanticipated conflicts. EMAs will be completed over 4 weeks. Participants will be compensated \$30 and \$60 for completion of baseline and end of treatment assessments (including a brief phone interview), respectively. Those who complete a brief phone interview at the end of treatment will be compensated an additional \$30. Participants can also receive bonus compensation for each online survey completed within 24 hours of being sent the link (\$5 at both baseline and the end of treatment).

Concerted efforts to keep retention high will include phone calls if incomplete EMAs are observed for more than 2 consecutive days, obtaining a functioning phone number, home address, and the name and phone number of 2 collaterals who can provide contact information if the participant is unreachable, and providing compensation for completing assessments, including increased compensation during later study periods.

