4.2.3. Aim 2: Measures

Baseline and end of treatment. At baseline and end of treatment, the self-reported following will be measured: Demographics (baseline only), smartphone-related information (e.g., operating system), smoking history/status,^{83,93} nicotine dependence using 2-item Heaviness of Smoking Index,^{84,94} smoking-related cognitive and affective processes (e.g., withdrawal symptoms),^{85,95-97} team developed measure of previous experience with contemplative practice developed for [name] study (used in Aim 1),⁸⁶ mindfulness using Avoidance and Inflexibility Scale,⁹⁸ Five Facet Mindfulness Questionnaires,⁹⁹ Self-Compassion Scale,¹⁰¹ affect using Positive and Negative Affect Schedule,¹⁰² depression using Patient Health Questionnaire, anxiety using Generalized Anxiety Disorder-7,¹⁰⁵ and cancer-relevant variables including pain, fatigue, and fear of cancer recurrence.¹⁰⁶⁻¹⁰⁸ Chart abstracted cancer variables (e.g., cancer type) will allow us to describe the heterogeneity in our sample. At the end of treatment, additional items will be assessed: smoking status, nicotine patch

PI: [name] use, changes in smartphone and/or carrier, perceived utility and acceptability of the mindEMI using team-developed items that were used in our team's previous studies (e.g., "How helpful were the mindful skills?")^{86,109-111} as well as validated measures.^{87,112-114} During the end of treatment interview,

open-ended questions on the mindEMI and feedback on the app and format of counseling (e.g., number of treatment sessions) will be assessed using the team developed items (e.g., "What did you like about using the app?").

[figure not shown]
App data. EMA measures will consist of self-reported items on state mindfulness using 3 items selected from extant validated measures,¹¹⁵⁻¹¹⁷ 6 affect items,^{102,118} 1 craving item ("I have an urge to smoke"), using a multiple-point Likert scale, and the number of cigarettes smoked and nicotine patch use (yes/no) as well as psychometrically sound cancer-specific items that include: 1 fatigue item (on a 11-point Likert scale),¹⁰⁷ 1 pain item (on a 11-point Likert scale),¹⁰⁶ and 1 item on fear of cancer recurrence (on a 4-point Likert scale).^{91,108,119,120} The EMAs can be completed in <2 minutes.

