7.2. Data Analysis

Aim 1. Two approaches of qualitative analysis will be used. First, the transcripts will be coded and key themes will be identified by 2 trained study staff. Texts will be analyzed for frequency (number of times the comment was mentioned), extensivity (number of participants making the comment), intensity (expressive strength of the comments), and specificity (degree of clear focus of the comment). A software, NVivo will be used to analyze the data. Coder agreement will be assessed using a Kappa statistic (\geq .80). Second, based on the principles of saturation in qualitative research, details of narratives will also be a focus of analyses. Qualitative analytic strategies such as immersion-crystallization will be implemented, in which the researcher reviews the data both intuitively and reflectively until the most relevant theme to the research questions arises. Descriptive analyses will be conducted on the data collected through survey and chart abstraction (M, SD, %).

Aim 2. The primary outcomes will be participants' open-ended feedback, and perceived utility and likability of the mindEMI based on the Aim 1 benchmarks and retention (\geq 75% through end of treatment). [name] will lead the qualitative thematic content analyses of the feedback and conduct descriptive analyses on usability measures (M, SD, %).

REFERENCES

1. US Department of Health and Human Services: Smoking Cessation: A report of the Surgeon General. Atlanta, GA, U.S. Department of Health and Human Services, Centers for Disease Control and Prevention, National Center for Chronic Disease Prevention and Health Promotion, Office on Smoking and Health, 2020

2. US Department of Health and Human Services: The health consequences of smoking—50 years of progress: a report of the Surgeon General, US Department of Health and Human Services, Centers for Disease Control and Prevention, National Center for Chronic Disease Prevention and Health Promotion, Office on Smoking and Health. Atlanta, GA, 2014

3. National Cancer Institute (NCI): Cancer survivors and smoking, 2018

4. Jassem J: Tobacco smoking after diagnosis of cancer: Clinical aspects. Transl Lung Cancer Res 8:S50, 2019

5. Guimond A-J, Croteau VA, Savard M-H, et al: Predictors of smoking cessation and relapse in cancer patients and effect on psychological variables: An 18-month observational study. Ann Behav Med 51:117-127, 2017

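### Does the 30-day smoking entry criterion undermine the 7-day abstinence measure in Aim 2?

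*Combined protocol and SAP*

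**What the plan says.** Section 3.1.1 sets the Aim 1 smoking criterion as "having smoked at least one cigarette (even one or two puffs) within the past 30 days". Section 3.2.1 carries it into Aim 2: "Recruitment and eligibility will mimic Aim 1, with the addition of a few eligibility criteria". Of the criteria added there, the one nearest to smoking behaviour is "Willing to give quitting a try as part of the study", which says nothing about when the person last smoked. Section 3.1.2 describes the source population: "Survivors who are current smokers will be recruited in 2 ways".

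For the outcome, section 4.2.2 states: "Smoking status will be measured using 7-day point prevalence of abstinence ([PPA]; no self-reported smoking in prior 7 days". Section 4.2.3 lists, among the self-reported items taken at both baseline and end of treatment, "smartphone-related information (e.g., operating system), smoking history/status". The app prompts also record the number of cigarettes smoked.

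Section 7.2 names the Aim 2 primary outcomes as open-ended feedback, perceived utility and likability, and retention of at least 75% through end of treatment. Its quantitative work for Aim 2 is to "conduct descriptive analyses on usability measures (M, SD" and percentages). Abstinence does not appear in that section.

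**The concern.** The entry window is 30 days and the outcome window is 7 days. An entrant can satisfy both at once: having smoked recently enough to be eligible, yet long enough ago to count as abstinent on the day of enrolment. If that person is also smoke-free in the week before the final survey, the definition classes them as abstinent although nothing has changed.

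In a single-arm cessation pilot, a reader might take an end-of-treatment abstinence percentage as the share who quit during the study. With 10 to 13 people and no control group, one or two such entrants would visibly move that percentage, and nothing else in the design would correct it. If the figure were then used to support a larger trial, it would mix new quitting with abstinence already present at entry.

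**Working it through.** **Do the two windows overlap?**

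- Eligible (3.1.1, applied to Aim 2 by 3.2.1): last smoking within 30 days before entry.
- Abstinent (4.2.2): no smoking in the prior 7 days.
- Both: last smoking 8 to 30 days before entry.

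No other text closes this. Sections 3.1.2, 4.1.2 and 7.1 describe the participants as people who smoke at present. Section 4.2.2 sets a quit date about a week after the first session, and section 4.2.5 relates the patch to the level of smoking. All of this presumes active smoking, but none of it sets a recency limit.

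**How far could one such entrant move a percentage?** The plan gives no abstinence figure to reproduce, so this shows scale only. Let n be the number assessed (10 completers or 13 recruited, section 7.1), k the number already 7-day abstinent at entry, and x the number who quit among those smoking at entry. The documents give neither k nor x; the values below are assumptions.

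- Crude percentage if the k entrants are smoke-free at the end: (x + k)/n
- Crude percentage if they are smoking at the end: x/n
- Percentage among baseline smokers: x/(n − k)

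With k = 1:

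| n | x | entrant at end | crude | among baseline smokers | difference (points) |
|---|---|---|---|---|---|
| 10 | 0 | smoke-free | 1/10 = 10.0% | 0/9 = 0% | +10.0 |
| 10 | 3 | smoke-free | 4/10 = 40.0% | 3/9 = 33.3% | +6.7 |
| 10 | 9 | smoke-free | 10/10 = 100% | 9/9 = 100% | 0 |
| 10 | 3 | smoking | 3/10 = 30.0% | 3/9 = 33.3% | −3.3 |
| 13 | 0 | smoke-free | 1/13 = 7.7% | 0/12 = 0% | +7.7 |
| 13 | 3 | smoke-free | 4/13 = 30.8% | 3/12 = 25.0% | +5.8 |
| 13 | 3 | smoking | 3/13 = 23.1% | 3/12 = 25.0% | −1.9 |

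With k = 0 the difference is zero. The n = 13 rows require every recruit to be assessed, whereas 13 are recruited so that 10 remain.

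**How likely is at least one such entrant?** If a share q of entrants were already 7-day abstinent, the chance of at least one among 10 is 1 − (1 − q)^10: 40% for q = 5%, 65% for 10%, 89% for 20% and 97% for 30%. These values of q are assumptions. Days 8 to 30 make up 23 of the 30 days in the entry window, but that is not a probability of enrolment: recruitment targets people recorded as smoking now.

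**Which planned result uses these percentages?** Sections 1 (Aim 2) and 7.2 agree on the primary outcomes: feedback, perceived utility and likability, and retention. None depends on smoking status at entry or at the end. Section 4.2.2 says how status is measured; no section says that a quit rate will be computed, compared or judged against a threshold.

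**Can the overlap be resolved from the data as planned?** Yes. Smoking status is taken at baseline and at end of treatment, and momentary assessments count cigarettes over four weeks that include a week before the quit date. For 10 to 13 people, baseline status against final status is a four-cell table or a short listing.

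**The case for a change.** The best argument for a change is that it would cost one sentence. The protocol has chosen to measure abstinence at the end of a cessation programme, section 7.2 has no rule for it, and fixing the denominator before data are seen would remove a later choice. Such entrants are also plausible: section 1 says that many survivors quit at diagnosis and that more than half of those who try resume within months. The reference to one or two puffs admits very light smokers, who may have a smoke-free week by chance.

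Much of this stands. The gap in the text is real, and wording about people who smoke now makes such an entrant less typical without excluding them. Two things weigh against acting on it.

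First, the sentence would govern an analysis that the plan does not contain. Section 1 rests the case for the later trial on feasibility and acceptability, not on an abstinence rate from 10 people. Point prevalence is also correctly applied: a person with no smoking in 7 days is abstinent by that definition, and the protocol never equates this with having quit during the study.

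Second, the obvious remedy has a flaw of its own. Restricting the quit percentage to those who smoked in the week before baseline, and calling the others maintained or relapsed, would mislabel intermittent smokers. Someone who smokes about every ten days could show a smoke-free week at baseline without ever having tried to quit, and the entry criterion deliberately admits such people.

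**Conclusion.** No change is needed. The entry and outcome windows do overlap, so an entrant could be 7-day abstinent at baseline. Followed as written, however, the plan produces no wrong result: abstinence is a descriptive measure with no planned percentage, benchmark or comparison, and the Aim 2 outcomes, recruitment and sample size are untouched.

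The possible distortion exists only in a crude percentage that someone might choose to report. In the examples above, one such entrant shifts it by between +10.0 and −3.3 points with 10 people, and by nothing if no such person enrols. That range rests on assumed counts, and it largely reflects the small sample: each of 10 people counts for 10 points whatever the reason.

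This is a gap that an analyst fills sensibly. Anyone describing final smoking status in so small a group would show it beside baseline status, from data already collected, and would not infer from one smoke-free week at baseline that the person had quit. The conclusion would differ if abstinence were a primary outcome, carried a threshold, or were the stated basis for the effect size of the next trial; none of these is so here.
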